3.8.2 Analysis of Secondary Endpoints for Safety

The safety secondary endpoints in this study target AEs related to islet transplantation (transplant procedure and/or islet product) and the immunosuppression and/or infection prophylaxis.

The targeted AEs related to the islet transplantation include:

1. AE-IIP-1: Bleeding (>2 g/dL decrease in hemoglobin concentration)
2. AE-IIP-2: Segmental portal vein thrombosis
3. AE-IIP-3: Biliary puncture
4. AE-IIP-4: Wound complication (infection or subsequent hernia)
5. AE-IIP-5: Increased transaminase levels (>5 times ULN)

The targeted AEs related to the immunosuppression and infection prophylaxis therapy include:

1. AE-IP-1: Allergy
2. AE-IP-2: Reduction in GFR
3. AE-IP-3: Increase in urinary albumin excretion
4. AE-IP-4: Addition or intensification of anti-hypertensive therapy
5. AE-IP-5: Addition or intensification of anti-hyperlipidemic therapy
6. AE-IP-6: Oral ulcers
7. AE-IP-7: Lower extremity edema
8. AE-IP-8: Gastrointestinal toxicity
9. AE-IP-9: Neutropenia, Anemia, or Thrombocytopenia
10. AE-IP-10: Viral, Bacterial, or Fungal Infections
11. AE-IP-11: Benign or Malignant Neoplasms

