3.8.2.1 Analyses at 75±5 days following the initial and final infusion

At 75±5 days following the initial and final islet transplant (if applicable), the incidence rates for each type of AE, grouped by severity, will be reported. For each type of AE, the number of resolved events will be counted as well. The mean, median, standard deviation and range for the number of days until the AE is resolved will be calculated. The results will be summarized in the table provided in SAP Appendix 2. Moreover, we will also report AEs categorized by attribution that is, AEs related to the islet transplant procedure or to immunosuppression; the report format is shown in SAP Appendix 3.

For second and third islet transplants, immunosuppression is modified by using Daclizumab (Zenapax[®]) instead of Thymoglobulin[®] for induction. For subjects who receive more than one islet transplant, we will compare the incidence rate at 75±5 days following the initial and final islet transplant for all AEs related to the islet transplant procedure and to immunosuppression one at a time using the McNemar's matched-pair test [8]. The claim of a difference in incidence rate will be made if the p-value is less

than 0.05. If the incidence is rare in certain severity categories for an AE, we will compare the incidence rate regardless the severity to accommodate the validity of the test.

The incidence rate of immune sensitization, defined as detection of anti-HLA antibodies at 75 ± 5 days following the initial and final islet transplant, (if applicable) will be reported. The exact two-sided 95% confidence interval of the incidence rate will also be reported.

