3.8.2.2 Analyses at 365±14 days following the initial and final infusion

At 365±14 days following the initial and final islet transplant (if applicable), the incidence rates for each type of AE, grouped by severity, will be reported. For each type of AE, the number of resolved events will be counted as well. The mean, median, standard deviation and range for the number of days until the AE is resolved will be calculated. The results will be summarized in the table provided in Appendix 3. Moreover, we will also report the individuals who incur the AEs related to the islet transplant procedure and immunosuppression therapy, and the report is given in the table described in Appendix 3.

For subjects who require more than one islet transplant, we will compare the incidence rate at 365±14 days following the initial and final islet transplant for all the AEs related to the islet transplant procedure and immunosuppression therapy one at a time using the McNemar's matched-pair test [8]. The claim of difference in incidence rate will be made if the p-value is less than 0.05. If AE incidence is rare in certain severity categories, we will compare the incidence rate regardless of the severity to accommodate the validity of the test.

Adverse events may require a change in the immunosuppression for an individual transplant recipient. We will document the number and proportion of participants who require such a change.

For subjects who do not present the anti-HLA antibodies prior to transplantation, we will calculate the incidence rate of immune sensitization defined by detecting anti-HLA antibodies at 365±14 days following the initial and final islet transplant, (if applicable). The exact two-sided 95% confidence interval of the incidence rate will also be reported.

At 365±14 days following the initial islet transplant, we will also assess the change in retinal photography from pre-transplant. The incidence rate of worsening retinopathy will be calculated and the exact two-sided 95% confidence interval of the rate will be provided.

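### The first-versus-final McNemar test has no rule for adverse events that persist from the first infusion, so equal risk can yield a false difference in either direction

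*SAP*

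**What the plan says.** Section 3.8.2 lists 16 targeted events: five tied to the islet transplant and eleven to immunosuppression and infection prophylaxis. Some are acute, such as bleeding, biliary puncture and infection. Others can last, for example "AE-IP-2: Reduction in GFR" and "AE-IP-5: Addition or intensification of anti-hyperlipidemic therapy".

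Section 3.8.2.1 opens the paired comparison with the change of induction agent: "For second and third islet transplants, immunosuppression is modified by using Daclizumab" in place of the first-transplant agent. Among subjects with more than one transplant, "we will compare the incidence rate at 75±5 days following the initial and final islet transplant", event by event, with McNemar's matched-pair test. The decision rule is formal: "The claim of a difference in incidence rate will be made" when p is below 0.05. Section 3.8.2.2 applies the same test at 365±14 days: "The claim of difference in incidence rate will be made if the p-value is less than 0.05".

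Neither section says how to treat an event that began after the first infusion and is still present. It could be counted again, leave the risk set, or count only if it worsens. No reference point is given for a reduction or an addition. By contrast, Section 3.8.2.2 limits the 365-day immune sensitization rate to subjects without anti-HLA antibodies before transplantation. The McNemar events carry no such restriction.

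**The concern.** McNemar's null hypothesis is that the two marginal rates are equal. That matches equal risk only if every subject can have the event afresh after each infusion. A subject who acquired a lasting event after the first infusion cannot do so. Counted by new onset, that subject enters as first-only and is never available for final-only. Counted by presence, the same subject enters as an event on both occasions, and only those still free can become discordant, all in the final-only direction. Either way the discordant pairs are unbalanced by the order of the infusions.

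The results at stake are prespecified claims on targeted safety endpoints. Because the induction change is mentioned immediately before the test, readers are likely to take a significant result as a comparison of induction regimens.

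**Working it through.** **Inputs.** From the SAP: McNemar's test per event, threshold 0.05, subjects with more than one transplant (Sections 3.8.2.1 and 3.8.2.2); 48 subjects in total, the upper limit for pairs (Section 2.4); final transplant no later than 8 months after the first (Section 3.1.1). The SAP does not give the number re-transplanted, N, or the event risk. I assume N=30 (also 20) and the same risk r in each window among subjects still at risk. Sidedness and test variant are not stated; I use the exact two-sided test.

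**The plan's own figures.** None exists for this comparison. As a check on the exact binomial arithmetic, 31 or more of 48 gives 0.8359 at a true rate of 0.70 and 0.0297 at 0.50, both as in Table 3.

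**Discordant-pair probabilities under equal risk.** Let b be first-only and c final-only.

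- A. New onset only, irreversible event: P(b)=r, P(c)=r(1-r).
- B. As A, but subjects with a prior event have a new one with probability r/2 (half can recur): P(b)=r(1-r/2), P(c)=r(1-r).
- C. Persisting event counted again: P(b)=0, P(c)=r(1-r).
- D. Fully repeatable, independent windows: P(b)=P(c)=r(1-r).

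Example for A with r=0.5, N=30: expected b=30×0.5=15 and c=30×0.5×0.5=7.5, so 50% against 25% although the risk is the same. Taken among subjects still at risk, the final rate is 7.5/15=50%.

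**Total probability of p<0.05**, summed over the trinomial distribution of b, c and concordant pairs, N=30:

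| r | A: new onset | B: half recur | C: counted again | D: repeatable |
|---|---|---|---|---|
| 0.1 | 1.2% | 1.1% | 4.8% | 1.0% |
| 0.2 | 3.2% | 2.5% | 35% | 2.2% |
| 0.3 | 6.7% | 3.6% | 62% | 2.5% |
| 0.4 | 14% | 5.8% | 76% | 2.7% |
| 0.5 | 27% | 9.5% | 80% | 2.8% |
| 0.6 | 51% | 17% | 76% | 2.7% |

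Under A, from r=0.3 upward nearly all of the error shows the final infusion lower (6.5 of 6.7 points at r=0.3). Under C all of it shows the final infusion higher. With N=20, A gives 9%, 18% and 35% at r=0.4, 0.5 and 0.6.

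**Test variant.** With N=24 and r=0.5 under A, the error in the final-lower direction is 0.227 with the exact test and 0.298 with the uncorrected chi-square, so the choice of variant does not remove the problem.

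**365 days.** With at most 8 months between first and final transplant, the two 12-month periods share at least 12−8=4 months. An onset in the shared period falls after both infusions. It enters both sides of the pair and drops out of the test as concordant, even for a repeatable event.

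**The case against.** Four points are fair.

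1. **Irreversibility is an extreme case.** Section 3.8.1 treats worsening as an adverse event, so a further fall in GFR can be a new event. The antihypertensive and lipid items include intensification as well as addition. Section 3.8.2.1 also counts resolved events. Column B reflects this: at r=0.4 to 0.6 the error falls by more than half, to about 6%, 9% and 17%. It still exceeds 5%.

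2. **Rare events are not harmed under onset counting.** At r of 0.2 or less the error stays below the nominal 5%, so neoplasm is a poor example.

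3. **The counting rule may sit elsewhere.** The SAP refers event collection and recording to protocol Section 8.2, and grading to the CIT-TCAE manual. Those may say whether an ongoing event is recorded again. They would then settle which column applies. Neither A nor C is a valid comparison of risk for a lasting event, so the choice of test would still be wrong.

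4. **Direction.** A reader might infer that the plan will produce a false claim that the later regimen is safer. The documents do not support that. The SAP fixes no counting rule, and counting persisting events again reverses the bias. It also provides for claiming a difference in incidence, not for a conclusion that one regimen is safer.

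**Conclusion.** The point stands in a direction-neutral form. For targeted events that can persist, the planned McNemar test does not test equal risk after the two infusions, and p<0.05 can signal a difference created by infusion order alone. With 30 re-transplanted subjects, new-onset counting of an irreversible event exceeds the nominal level from about r=0.3 (7%) and reaches 51% at r=0.6; partial recurrence lowers this substantially. Counting persisting events again does more damage at lower risks: 35% at r=0.2. These sizes rest on an assumed N and r and on equal risk across subjects. For events that can recur independently, the 75-day test keeps its level. The 365-day comparison has the further defect of overlapping windows. Only secondary safety claims are affected; the primary analysis is untouched.

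**What to change.** Classify all 16 targeted events in advance as acute and repeatable or as lasting, including lower extremity edema and the cytopenias, and state for each what counts as a new event and against which reference point.

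Keep the McNemar test and its p<0.05 claim only for acute, repeatable events, with a new onset required in the 75-day window after each infusion.

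For lasting events, and for all events over the overlapping 365-day windows, make no first-versus-final claim. Report new onset or worsening after the final infusion among subjects free of the event at that infusion, with exact intervals, as description. State that those still at risk may be less susceptible than the group at first infusion, so the two rates are not a comparison of regimens even with the corrected denominator.

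The cost is SAP wording, a changed denominator and fewer formal claims on secondary safety events. No new data are needed.

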3.8.2.2 Analyses at 365±14 days following the initial and final infusion

At 365±14 days following the initial and final islet transplant (if applicable), the incidence rates for each type of AE, grouped by severity, will be reported. For each type of AE, the number of resolved events will be counted as well. The mean, median, standard deviation and range for the number of days until the AE is resolved will be calculated. The results will be summarized in the table provided in Appendix 3. Moreover, we will also report the individuals who incur the AEs related to the islet transplant procedure and immunosuppression therapy, and the report is given in the table described in Appendix 3.

For subjects who require more than one islet transplant, we will compare the incidence rate at 365±14 days following the initial and final islet transplant for all the AEs related to the islet transplant procedure and immunosuppression therapy one at a time using the McNemar's matched-pair test [8]. The claim of difference in incidence rate will be made if the p-value is less than 0.05. If AE incidence is rare in certain severity categories, we will compare the incidence rate regardless of the severity to accommodate the validity of the test.

Adverse events may require a change in the immunosuppression for an individual transplant recipient. We will document the number and proportion of participants who require such a change.

For subjects who do not present the anti-HLA antibodies prior to transplantation, we will calculate the incidence rate of immune sensitization defined by detecting anti-HLA antibodies at 365±14 days following the initial and final islet transplant, (if applicable). The exact two-sided 95% confidence interval of the incidence rate will also be reported.

At 365±14 days following the initial islet transplant, we will also assess the change in retinal photography from pre-transplant. The incidence rate of worsening retinopathy will be calculated and the exact two-sided 95% confidence interval of the rate will be provided.

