2.3.2.3 Safety endpoints

At 75 ± 5 days following each transplant and 365 ± 14 days following the first and final islet transplant(s):

- The incidence and severity of adverse events (AEs) related to the islet transplant procedure, including: bleeding (>2 g/dL decrease in hemoglobin concentration); segmental portal vein thrombosis; biliary puncture; wound complication (infection or subsequent hernia); and increased transaminase levels >5 times upper limit of normal (ULN)
- The incidence and severity of AEs related to the immunosuppression including: allergy; reduction in glomerular filtration rate (GFR); increase in urinary albumin excretion; addition or intensification of anti-hypertensive therapy; addition or intensification of anti-hyperlipidemic therapy; oral ulcers; lower extremity edema; gastrointestinal toxicity; neutropenia, anemia, or thrombocytopenia; viral, bacterial, or fungal infections; and benign or malignant neoplasms
- The incidence of change in the immunosuppression drug regimen
- The incidence of immune sensitization defined by presence of anti-HLA (histocompatibility antigen) antibodies absent prior to transplantation

At 365 ± 14 days following the first islet transplant:

- The incidence of worsening retinopathy as assessed by change in retinal photography

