4.2.2 Site Suspension and Review

Criteria for suspension of study enrollment and initial islet infusions at individual sites are detailed in the CIT-07 protocol, section 6.2.2.

After any site is placed on hold, no additional transplants will be performed at that site until the CIT Steering Committee and DSMB meet either in person or by conference call to review in depth the results and circumstances surrounding the islet functional failure or SAE to determine whether the trial enrollment of new subjects and conduct of additional transplants could be safely resumed at that site, or whether there could be implications for the continuation of the entire proposed pilot protocol also at other affiliated sites testing the same protocol.

In all cases of PNF, subjects will be asked to temporarily continue immunosuppression to decrease the risk of sensitization that could increase the risk of poor outcome should future transplants occur. A tapering schedule will be applied until immunosuppressants are completely discontinued.

Reference

- [7] Steja D. Can continuous glucose monitoring provide objective documentation of hypoglycemia unawareness? *Endocr Pract.* 2005; 11(2):83-90.

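### The planned analysis of immunosuppression change is narrower than the SAP's own safety endpoint: it counts only changes that adverse events require, and it gives no Day 75 figure.

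*SAP*

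**What the plan says.** Section 2.3.2.3 lists four safety endpoints under a shared pair of time points: 75 ± 5 days after each transplant, and 365 ± 14 days after the first and the final transplant. The third is "The incidence of change in the immunosuppression drug regimen". The two endpoints listed before it are expressly about adverse events related to the procedure or to the drugs. This one carries no such qualifier.

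Section 3.8.2.2, which covers the Day 365 safety analyses, contains the only analysis of this endpoint, in two sentences: "Adverse events may require a change in the immunosuppression for an individual transplant recipient." and then "We will document the number and proportion of participants who require such a change."

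Section 3.8.2.1, which covers the Day 75 safety analyses, plans adverse-event incidence and resolution, matched-pair comparisons between the initial and final transplant, and a sensitization rate ("The incidence rate of immune sensitization, defined as detection of anti-HLA antibodies at 75 ± 5 days following the initial and final islet transplant"). It plans nothing on regimen change.

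The SAP also mentions changes whose cause is something else, or is not stated to be an adverse event. Section 3.8.2.1 notes a planned one: "For second and third islet transplants, immunosuppression is modified by using Daclizumab". Section 4.2.2 describes what follows primary non-function: "A tapering schedule will be applied until immunosuppressants are completely discontinued."

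**The concern.** Section 3.3.2 defines the treatment under study as the transplant together with its immunosuppression. In a single-arm trial, the frequency with which that regimen was altered is a direct description of how well the package could be maintained. The endpoint asks for that frequency, whereas the analysis sentence asks for the part of it that adverse events forced.

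Two things follow if the SAP is applied as written. A subject whose regimen changed only for another reason does not enter the numerator, so the published proportion may be read as the endpoint when it is a subset of it. In addition, one of the two stated time points has no figure, so the report cannot show how many changes came early.

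There is also a reproducibility problem. The SAP does not say whether withdrawal after graft failure counts, or whether the scheduled switch of induction agent counts. Two analysts could return different numbers from the same data.

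**Working it through.** There is no figure in the SAP to reproduce, since no rate of regimen change is stated or assumed anywhere. The check is a comparison of texts, followed by one inequality.

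| Element | Endpoint (2.3.2.3) | Analysis (3.8.2.1 and 3.8.2.2) |
|---|---|---|
| Cause of change | Not restricted | Change required by an adverse event (3.8.2.2) |
| Day 75 | After each transplant | None |
| Day 365 | After the first and final transplant | Number and proportion, in the section headed for the initial and final infusion |
| Table template | – | No row in Appendices 2–5, 9 or 10 |

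**Cause.** The demonstrative in "We will document the number and proportion of participants who require such a change" needs an antecedent. The sentence before it supplies one, a change that an adverse event has made necessary. Nothing else in the section mentions a regimen change.

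**Direction.** Let N be the number of subjects analysed, C the number with a regimen change for any reason, and A the number with at least one change that an adverse event required. Every subject in A is also in C, so

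A/N ≤ C/N.

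Let s be the share of the C subjects whose changes were all for other reasons. Then

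A/N = (1 − s) × C/N.

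With s = 0 the two proportions agree. With any s above 0 the reported one is lower. The SAP gives no value for s or for C, so the gap cannot be computed. For scale only, with the planned 48 subjects each subject left out is 1/48 = 2.1 percentage points.

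**Timing.** The Day 75 section has no sentence on this endpoint, so the separate Day 75 proportion does not exist in the plan. The Day 75 section is also organised around the initial and final transplant, whereas the endpoint says each transplant. With up to three transplants allowed (section 3.1.1), a second transplant that is followed by a third would be missed even if a Day 75 sentence were added under the present heading.

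**Planned changes.** Read literally, the endpoint would also count every re-transplanted subject, because the induction agent is scheduled to differ. This would mix a design feature with departures from the regimen, so the endpoint itself needs a rule on it.

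**The case against.** The strongest reply is that the adverse-event sentence in section 3.8.2.2 is only motivation, and that the count was meant to cover any change in immunosuppression. No word such as *only* appears. Alternatively, section 3.8.2 opens by saying that the safety endpoints are aimed at adverse events, so an adverse-event count may be what was intended throughout. Either intention is possible. However, the first is not what the sentence says, and the second conflicts with the unqualified endpoint in section 2.3.2.3. Both readings call for the same clarification.

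A second reply is that primary non-function may itself be an adverse event. The definition in section 3.8.1 is broad and includes abnormal laboratory findings, so the taper in section 4.2.2 could already be in the count. This stands as an open question. Sections 4.2.1 and 4.2.2 name islet functional failure alongside serious adverse events as separate matters for review. That separates it from *serious* events, but it does not settle whether it is an adverse event. The taper therefore illustrates the ambiguity and does not prove an omission.

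A third reply is that some of the information appears elsewhere. Major deviations that alter study therapy are summarised (section 3.5), and the regimen and treatment duration are listed for subjects who terminate early (section 3.4). This is true, but neither gives the incidence that the endpoint calls for.

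The lack of a confidence interval is not a defect. The neighbouring sensitization and retinopathy rates get exact intervals, but the endpoint asks only for an incidence, and a number and proportion supply one.

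**Conclusion.** The mismatch is in the text and is worth correcting. The analysis in section 3.8.2.2 covers a subset of the endpoint in section 2.3.2.3, and section 3.8.2.1 omits it. The reported Day 365 proportion can only equal or fall below the defined one. This conclusion rests on reading the demonstrative in section 3.8.2.2 by its plain antecedent. It needs no numerical assumption.

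A reader might infer more than this in three ways:

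- **That the incidence is definitely understated.** It is understated only if some subjects have changes solely for reasons other than adverse events, and the SAP does not say how many will.
- **That the shortfall can be sized from expected treatment failures.** It is tempting to start from the 24 to 30% who would miss the primary endpoint at a 70 to 76% favorable rate (about 12 to 14 of 48) and assume that some fraction stop their drugs. The base is wrong. A subject can miss that composite through HbA1c, one severe hypoglycemic event or a missing evaluation while staying on immunosuppression. The SAP also gives no fraction. No such magnitude should be quoted.
- **That all information on early changes is lost.** The Day 365 count has no start limit, so a change before Day 75 can still be in it. What is missing is the separate Day 75 figure.

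The point concerns a reported safety result. It has no bearing on the primary analysis.

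**What to change.** Amend sections 3.8.2.1 and 3.8.2.2 so that both report the number and proportion of subjects with any change in the immunosuppression regimen, whatever the reason, at Day 75 after each transplant and at Day 365 after the first and final transplant.

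- Break the count down by reason: adverse event; graft failure, including any taper after primary non-function; other. The count of changes required by adverse events is kept as the first sub-category.
- Tabulate the protocol-specified change of induction agent at second and third transplants separately, so that it neither inflates the main count nor disappears.
- Add a table template, since none of the present appendices has a row for this endpoint.
- Optionally, attach an exact two-sided 95% interval, as is done for the sensitization and retinopathy rates.

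The cost is a few sentences in the SAP and one table. The breakdown needs a recorded reason for each change. The SAP does not say whether that field is collected, so this should be checked before the wording is fixed. The change affects reporting only and alters no treatment rule.
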